5.2 Study Calendar: Schedule 1 (¹⁷⁷Lu-PSMA-617 prior to Pembrolizumab)

	Screening (Day -28 to -1 unless otherwise noted)	Treatment				End of Treatment	Safety Follow up			
		Cycle 1			Cycle 2+ (+/- 3 days unless otherwise noted)		D1 (+/- 3 days)	+ 21 days	30 Days (+/- 7 days) post-last dose	
		D1 (-3 days)	D2	D8 (+/- 1 day)						
Informed consent	x									
Medical history	x									
Baseline conditions	x									
Concurrent medications	x	x		x	x	x	x	x	x	
Height	x									
Weight	x	x		x	x	x	x	x	x	
ECOG Performance status	x	x		x	x	x	x	x	x	
Physical exam and vital signs	x	x		x	x	x	x	x	x	
CBC and Serum Chemistry Panel^{1,2}	x	x		x	x	x ³	x	x	x	
Thyroid function tests^{2,4}	x					x	x	x	x	
PSA²	x	x				x	x	x	x	
Testosterone	x									
⁶⁸Ga-PSMA-11 PET/CT or PET/MR	x ⁵						x			
Disease assessment	x					x	x			

¹ Chemistry panel to include: sodium, potassium, chloride, bicarbonate, BUN/creatinine, glucose, calcium, total bilirubin, AST, ALT, alkaline phosphatase

² Labs may be collected within a window of up to 3 days prior to each dose of pembrolizumab.

³ CBC + differential will be measured on C1D1, C1D8, C1D15, C2D1, C2D8, C2D15, Day 1 of C3+, and additionally as clinically indicated.

⁴ TSH (with reflex free T3/T4) testing to be performed during Screening, Cycle 2 Day 1, and Day 1 of every other cycle thereafter.

⁵ Allow for a 12-week window for the screening PSMA PET scan. PSMA PET at End of Treatment is optional.

	Screening (Day -28 to -1 unless otherwise noted)	Treatment				End of Treatment	Safety Follow up		
		Cycle 1			Cycle 2+ (+/- 3 days unless otherwise noted)		30 Days (+/- 7 days) post-last dose	90 Days (+/- 14 days) post last dose	
		D1 (-3 days)	D2	D8 (+/- 1 day)	D15 (+/- 1 day)	D1 (+/- 3 days)	+ 21 days		
(CT/MR, BS) ⁶									
Tumor Biopsy ⁷	x				x				
Whole blood for immune correlatives ⁸		x			x	x			
¹⁷⁷ Lu-PSMA-617 infusion		x							
SPECT/CT Dosimetry ⁹			x						
Normal Saline		x							
Anti-emetic pre-medication		x							
Pembrolizumab infusion					x				
AE assessment		x	x	x	x	x	x	x	x

⁶ Tumor assessment will be performed with CT chest/and/pelvis + whole body bone scan during Screening, C4D1 (-14d), C7D1 (-14d), and Day 1 (-14d) of every 4 cycles thereafter. If disease progression by RECIST 1.1/PCWG3, confirmatory scans are required \geq 4 weeks following first scan showing progression.

⁷ Tumor biopsy will be performed during Screening and within 7 days preceding C2D1 visit. Screening biopsy must be performed prior to initiation of study treatment but is not subject to 28-day screening window. Bone biopsies are acceptable if no soft tissue lesion is amenable for biopsy. The same lesion should be selected for the follow up biopsy whenever feasible.

⁸ Whole blood (40 mL in Na-Heparin green top tube) will be collected on C1D1 (pre-dose), C2D1 (pre-dose), C3D1 (pre-dose), on Day 1 of every 3 cycles thereafter (e.g. C6D1, C9D1, etc), and at the time of disease progression

⁹ SPECT/CT dosimetry scan is optional.

5.3 Study Calendar – Schedule 2 (Concurrent Dosing)

	Screening (Day -28 to -1 unless otherwise noted)	Treatment				End of Treatment	Safety Follow up		
		Cycle 1			Cycle 2+ (+/- 3 days unless otherwise noted)		D1 (+/- 3 days)	+ 21 days	30 Days (+/- 7 days) post-last dose
		D1 (-3 days)	D2	D8 (+/- 1 day)	D15 (+/- 1 day)				
Informed consent	x								
Medical history	x								
Baseline conditions	x								
Concurrent medications	x	x		x	x	x		x	x
Height	x								
Weight	x	x		x	x	x	x	x	x
ECOG Performance status	x	x		x	x	x	x	x	x
Physical exam and vital signs	x	x		x	x	x	x	x	x
CBC and Serum Chemistry Panel^{1,2}	x	x		x	x	x ³	x	x	x
Thyroid function tests^{2,4}	x					x	x	x	x
PSA²	x	x				x	x	x	x
Testosterone	x								
⁶⁸Ga-PSMA-11 PET/CT or PET/MR	x ⁵						x		
Disease assessment (CT/MR,	x					x	x		

¹ Chemistry panel to include: sodium, potassium, chloride, bicarbonate, BUN/creatinine, glucose, calcium, total bilirubin, AST, ALT, alkaline phosphatase

² Labs may be collected within a window of up to 3 days prior to each dosing of pembrolizumab.

³ CBC + differential will be measured on C1D1, C1D8, C1D15, C2D1, C2D8, C2D15, Day 1 of C3+, and additionally as clinically indicated.

⁴ TSH (with reflex free T3/T4) testing to be performed during Screening, Cycle 1 Day 1, Cycle 2 Day 1, and Day 1 of every other cycle thereafter.

⁵ Allow for a 12-week window for the screening PSMA PET scan. PSMA PET scan at End of Treatment is optional.

	Screening (Day -28 to -1 unless otherwise noted)	Treatment				End of Treatment	Safety Follow up	
		Cycle 1			Cycle 2+ (+/- 3 days unless otherwise noted)		D1 (+/- 3 days)	+ 21 days
		D1 (-3 days)	D2	D8 (+/- 1 day)	D15 (+/- 1 day)			
BS) ⁶								
Tumor Biopsy ⁷	x				x			
Whole blood for immune correlatives. ⁸		x			x	x		
¹⁷⁷ Lu-PSMA-617 infusion		x						
SPECT/CT Dosimetry ⁹			x					
Normal Saline		x						
Anti-emetic pre-medication		x						
Pembrolizumab infusion		x			x			
AE assessment		x		x	x	x	x	x

⁶ Tumor assessment will be performed with CT chest/and/pelvis + whole body bone scan during Screening, C4D1 (-14d), C7D1 (-14d), and Day 1 (-14d) of every 4 cycles thereafter. If disease progression by RECIST 1.1/PCWG3, confirmatory scans are required \geq 4 weeks following first scan showing progression.

⁷ Tumor biopsy will be performed during Screening and within 7 days preceding C2D1 visit. Screening biopsy must be performed prior to initiation of study treatment but is not subject to 28-day screening window. Bone biopsies are acceptable if no soft tissue lesion is amenable for biopsy. The same lesion should be selected for the follow up biopsy whenever feasible.

⁸ Whole blood (40 mL in Na-Heparin green top tube) will be collected on C1D1 (pre-dose), C2D1 (pre-dose), C3D1 (pre-dose), on Day 1 of every 3 cycles thereafter (e.g. C6D1, C9D1, etc), and at the time of disease progression.

⁹ SPECT/CT dosimetry scan is optional.

5.4 Study Calendar – Schedule 3 (¹⁷⁷Lu-PSMA-617 following Pembrolizumab)

	Screening (Day -49 to -21 unless otherwise noted)	Treatment						End of Treatment	Safety Follow up	
		Cycle 1					Cycle 2+ (+/- 3 days unless otherwise noted)	D1 (+/- 3 days)	+ 21 days	30 Days (+/- 7 days) post-last dose
		D-21 (-3 days)	D1 (- 3 days)	D2	D8 (+/- 1 day)	D15 (+/- 1 day)				
Informed consent	x									
Medical history	x									
Baseline conditions	x									
Concurrent medications	x	x	x		x	x	x		x	x
Height	x									
Weight	x	x	x		x	x	x	x	x	x
ECOG Performance status	x	x	x		x	x	x	x	x	x
Physical exam and vital signs	x	x	x		x	x	x	x	x	x
CBC and Serum Chemistry Panel^{1,2}	x	x	x		x	x	x ³	x	x	x
Thyroid function tests^{2,4}	x	x					x	x	x	x
PSA²	x	x	x				x	x	x	x
Testosterone	x									
⁶⁸Ga-PSMA-11 PET/CT or PET/MR⁵	x ⁵							x		

¹ Chemistry panel to include: sodium, potassium, chloride, bicarbonate, BUN/creatinine, glucose, calcium, total bilirubin, AST, ALT, alkaline phosphatase

² Labs may be collected within a window of up to 3 days prior to each dosing of pembrolizumab.

³ CBC + differential will be measured on C1D1, C1D8, C1D15, C2D1, C2D8, C2D15, Day 1 of C3+, and additionally as clinically indicated.

⁴ TSH (with reflex free T3/T4) testing to be performed during Screening, Cycle 1 Day 1, Cycle 2 Day 1, and Day 1 of every other cycle thereafter.

⁵ Allow for a 12-week window for the screening PSMA PET scan. PSMA PET scan at End of Treatment is optional.

Disease assessment (CT/MR, BS) ⁶	x						x	x			
Tumor Biopsy ⁷	x						x				
Whole blood for immune correlates ⁸		x	x				x	x			
¹⁷⁷ Lu-PSMA-617 infusion			x								
SPECT/CT Dosimetry ⁹				x							
Normal Saline			x								
Anti-emetic pre-medication			x								
Pembrolizumab infusion		x	x				x				
AE assessment		x	x		x	x	x	x	x	x	x

⁶ Tumor assessment will be performed with CT chest/and/pelvis + whole body bone scan during Screening, C4D1 (-14d), C7D1 (-14d), and Day 1 (-14d) of every 4 cycles thereafter. If disease progression by RECIST 1.1/PCWG3, confirmatory scans are required \geq 4 weeks following first scan showing progression.

⁷ Tumor biopsy will be performed during Screening and within 14 days preceding C3D1 visit. Screening biopsy must be performed prior to initiation of study treatment but is not subject to 28-day screening window. Bone biopsies are acceptable if no soft tissue lesion is amenable for biopsy. The same lesion should be selected for the follow up biopsy whenever feasible. PSMA-avid lesion should be prioritized for biopsy; non-PSMA avid lesion may be used if no PSMA-avid lesion is accessible.

⁸ Whole blood (40 mL in Na-Heparin green top tube) will be collected on C1D-21 (pre-dose), C1D1 (pre-dose), C2D1 (pre-dose), C3D1 (pre-dose), on Day 1 of every 3 cycles thereafter (e.g. C6D1, C9D1, etc), and at the time of disease progression.

⁹ SPECT/CT dosimetry scan is optional.

6 Reporting and Documentation of Results

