2.1 Objectives

Primary Objectives

Part A: To determine the recommended phase 2 dose and schedule of ¹⁷⁷Lu-PSMA-617 in combination with pembrolizumab in patients with mCRPC.

Part B (Dose Expansion): To determine the objective response rate by RECIST 1.1 criteria.

Secondary Objectives

1. To characterize the safety profile of the combination.
2. To determine the median duration of response by RECIST 1.1 criteria.
3. To determine the proportion of patients who experience $\geq 50\%$ decline from baseline in serum PSA.
4. To determine the median PSA progression-free survival.
5. To determine the median time to symptomatic skeletal related event.
6. To determine the 6 month radiographic progression-free survival rate and median radiographic progression-free survival.
7. To determine the median overall survival.

Correlative Objectives

1. To assess the lesion-specific response rate by baseline PSMA avidity on ⁶⁸Ga-PSMA-11 PET.
2. To quantify the change from baseline in T cell repertoire, circulating T cell subsets, tumor infiltrating lymphocytes, and tumor PD-L1 expression by immunohistochemistry after one priming dose of Lu-PSMA RLT.
3. To explore the relationship between timing of the ¹⁷⁷Lu-PSMA-617 priming dose with initiation of pembrolizumab with respect to immunologic, safety, and efficacy outcomes.
4. To descriptively characterize the patterns of uptake on ⁶⁸Ga-PSMA-11 PET at the time of disease progression.
5. To explore relationship between tumor genomic profile with clinical outcomes including response rate and progression-free survival.
6. To explore the relationship between tumor dosimetry with objective response.

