3.1 Characteristics

This is a single-center Phase 1b open-label, study of PSMA-targeted radionuclide therapy with ¹⁷⁷Lu-PSMA-617 in combination with pembrolizumab in patients with mCRPC who have previously progressed on at least one prior androgen pathway inhibitor (e.g. abiraterone, enzalutamide, apalutamide). Patients must have at least three metastatic lesions which are PSMA-avid on baseline ⁶⁸Ga-PSMA-11 PET imaging.

In **Part A** of the study, patients will be enrolled in sequential fashion to one of treatment schedules with respect to timing of ¹⁷⁷Lu-PSMA-617 in relation to first dose of pembrolizumab (N = 6 evaluable patients per schedule):

Schedule 1) Priming dose of ¹⁷⁷Lu-PSMA-617 administered on Cycle 1 Day 1 followed by pembrolizumab 200 mg IV q 21 days starting Cycle 2 Day 1.

Schedule 2) Priming dose of ¹⁷⁷Lu-PSMA-617 administered concurrently with initiation of pembrolizumab on Cycle 1 Day 1.

Schedule 3) Priming dose of ¹⁷⁷Lu-PSMA-617 administered on Cycle 1 Day 1 following initiation of pembrolizumab on Cycle 1 Day -21.

The priming dose of ¹⁷⁷Lu-PSMA-617 will be 7.4 +/- 15% GBq, which is the recommended phase 3 dose of the agent. If the DLT frequency exceeds 33% including patients across the three schedules, Dose Level -1 of ¹⁷⁷Lu-PSMA-617 will be investigated (4 Gbq +/- 15%).

6 evaluable patients will be enrolled in each of the three cohorts in sequential fashion in Part A of the study. The DLT window will be Cycle 1 + Cycle 2. If the DLT frequency is \geq 33% for a

particular cohort, that dosing schedule will be determined to be non-tolerable and the next schedule will be evaluated. In addition, if the DLT frequency attributable specifically to Lu-PSMA-617 is $\geq 33\%$ after 6 or more evaluable patients are enrolled in Part A of the study, the dose of Lu-PSMA-617 will be reduced to Dose Level -1 (4 GBq +/- 15%) for the remainder of patients enrolled on study. If the DLT frequency attributable to Lu-PSMA-617 at Dose Level -1 is $\geq 33\%$ after 6 or more patients are treated at Dose Level -1, study accrual will be halted.

Using the data obtained in Part A, the recommended phase 2 dose and schedule of ^{177}Lu -PSMA-617 will be determined by the DSMC and Principal Investigator using a combination of safety, efficacy, and immunologic effects of treatment from the first two cycles (and additional cycles of treatment when available).

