3.3 Eligibility Criteria

Patients must have baseline evaluations performed prior to Cycle 1 Day 1 of treatment and must meet all inclusion and none of the exclusion criteria. In addition, the patient must be thoroughly informed about all aspects of the study, including the study visit schedule and required evaluations and all regulatory requirements for informed consent. The written informed consent must be obtained from the patient prior to enrollment. The following criteria apply to all patients enrolled onto the study unless otherwise specified.

Inclusion Criteria

Part A:

- (1) The subject is able and willing to comply with study procedures and provide signed and dated informed consent.
- (2) Male participants who are at least 18 years of age on the day of signing informed consent.

(3) Histologically confirmed prostate adenocarcinoma. *De novo* small cell neuroendocrine prostate cancer will not be allowed due to putative lower PSMA expression in this tumor subtype. Treatment-emergent small cell neuroendocrine prostate cancer detected in metastatic tumor biopsy is not an exclusion.

(4) A minimum of three PSMA-avid lesions on baseline ^{68}Ga -PSMA-11 PET, with positive lesions defined as those with SUV_{max} values greater than liver.

(5) Progressive metastatic castration-resistant prostate cancer by PCWG3 criteria at the time of study entry.

(6) Castrate level of serum testosterone at study entry (< 50 ng/dL). Patients without prior bilateral orchiectomy are required to remain on LHRH analogue treatment for duration of study

(7) Prior progression on at least one second generation androgen signaling inhibitor including abiraterone, apalutamide, darolutamide, and/or enzalutamide.

(8) Adequate hematologic, renal, and liver function, defined as:

- Absolute neutrophil count $> 1.5 \times 10^9/\text{L}$
- Hemoglobin $> 9.0 \text{ g/dL}$
- Platelet count $> 100,000/\text{microliter}$
- Serum creatinine $\leq 1.5 \times \text{ULN}$ or estimated GFR $> 50 \text{ ml/min}$ by Cockcroft-Gault or 24 hour urine collection.
- Total bilirubin $\leq 1.5 \times \text{ULN}$. In patients with known or suspected Gilbert's disease, direct bilirubin $\leq \text{ULN}$.
- Aspartate aminotransferase and alanine aminotransferase $\leq 2.5 \times \text{ULN}$ ($\leq 5 \times \text{ULN}$ in patients with liver metastases).

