(9) No other systemic anti-cancer therapies administered other than LHRH analogue within 14 days, or 5 half-lives, whichever is shorter, prior to initiation of study treatment. Adverse events related to prior anti-cancer treatment other than LHRH analog treatment must have recovered to Grade ≤ 1 with the exception of any grade alopecia and grade ≤ 2 neuropathy.

(10) Patients must have an ECOG performance status of 0 or 1.

(11) Patients must use appropriate methods of contraception during study treatment and for at least 60 days after last study treatment.

- Patients who are sexually active should consider their female partner to be of childbearing potential if she has experienced menarche and is not postmenopausal (defined as amenorrhea > 24 consecutive months) or has not undergone successful surgical sterilization. Even women who

use contraceptive hormones (oral, implanted, or injected), an intrauterine device, or barrier methods (diaphragms, condoms, spermicide) should be considered to be of childbearing potential.

- Patients who have undergone vasectomy themselves should also be considered to be of childbearing potential.
- Acceptable methods of contraception include continuous total abstinence, or double-barrier method of birth control (e.g. condoms used with spermicide, or condoms used with oral contraceptives). Periodic abstinence and withdrawal are not acceptable methods of contraception.

(12) Patients must provide consent to comply to recommended radioprotection precautions during study

(13) Patients willing to undergo tumor biopsy and have at least one lesion safely accessible to tumor biopsy. Bone or soft tissue lesion is allowed.

(14) Measurable disease by RECIST 1.1 criteria

Exclusion Criteria

- (1)** Untreated brain metastases at study entry. Patients with previously treated brain metastases are eligible provided the following criteria are all met:
 - Last treatment was > 28 days prior to C1D1
 - No evidence of new/progressive brain metastases is observed on MRI obtained during Screening window
 - Patient is clinically stable without requirement of steroid treatment for at least 14 days prior to first dose of study treatment.
- (2)** Receipt of prior PSMA-directed treatment (e.g. radiotherapy, immunotherapy, or antibody-drug conjugate).
- (3)** Prior enrollment on clinical study investigating Lu-PSMA-based radioligand therapy
- (4)** Prior treatment with radium-223 or other radioisotope for the treatment of prostate cancer.

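### Only the Schedule 3 calendar gives PSMA-avid lesions priority for biopsy, which could dilute the tissue immune results and add a lesion-selection difference between schedules

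*Combined protocol and SAP*

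**What the plan says.** Footnote 7 governs biopsies in all three study calendars. Each version accepts bone only when no soft-tissue lesion is amenable, and each adds "The same lesion should be selected for the follow up biopsy whenever feasible". Only the Schedule 3 version (5.4) continues: "PSMA-avid lesion should be prioritized for biopsy; non-PSMA avid lesion may be used if no PSMA-avid lesion is accessible".

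No other section supplies an avidity rule for the biopsied lesion. In Section 3.3, inclusion 13 asks that patients "have at least one lesion safely accessible to tumor biopsy. Bone or soft tissue lesion is allowed". Inclusion 4 requires "A minimum of three PSMA-avid lesions on baseline" PET, with avid meaning SUVmax above liver. It does not require every lesion, or the biopsied one, to be avid.

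The tissue data have two uses. Correlative objective 2 (Section 2.1), which concerns the effect of the single Lu-PSMA priming dose, is "To quantify the change from baseline in T cell repertoire, circulating T cell subsets, tumor infiltrating lymphocytes, and tumor PD-L1 expression by immunohistochemistry". Correlative objective 3 explores how the timing of the priming dose relates "with initiation of pembrolizumab with respect to immunologic, safety, and efficacy outcomes". Section 3.1 has the recommended dose and schedule chosen "using a combination of safety, efficacy, and immunologic effects of treatment from the first two cycles". Section 8.4.3 plans descriptive statistics for the immune changes. It plans no test between schedules and makes no use of the biopsied lesion's avidity.

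**The concern.** The protocol itself treats avidity as relevant lesion by lesion. Section 1.3 stresses that PSMA expression varies across metastases, and Section 8.4.3 relates each target lesion's uptake to its own response. A lesion with little PSMA can be expected to receive little direct radiation from the drug. If its immune change is smaller, including such lesions lowers the average tissue change. If they are more common under one schedule than another, the schedules will appear to differ for a reason unrelated to timing.

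Schedules 1 and 2 leave a concrete route to this. Their only baseline preference is soft tissue over bone, so a non-avid node could be taken ahead of an avid bone lesion in the same patient. Three avid lesions per patient do not prevent it.

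At stake are the tissue part of objective 2, one input to the schedule choice, and the paired biopsies that Section 1.7.1 gives as a reason for raising Part B from 12 to 25 patients.

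**Working it through.** The plan states no figure on this point, so there is none to reproduce. The check compares the texts and then illustrates the possible size.

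**Step 1. The biopsy rules side by side (footnote 7; dosing from the same calendars).**

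| | Schedule 1 | Schedule 2 | Schedule 3 |
|---|---|---|---|
| Soft tissue before bone | yes | yes | yes |
| Same lesion at follow-up if feasible | yes | yes | yes |
| Avid lesion first | not stated | not stated | yes, non-avid as fallback |
| Follow-up biopsy window | 7 days before C2D1 | 7 days before C2D1 | 14 days before C3D1 |
| Approximate day, priming dose = day 1 | 15–22 | 15–22 | 29–43 |
| Scheduled pembrolizumab doses before it | 0 | 1 | 3 |

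**Step 2. Dilution within a schedule.** Let D be the mean change in avid lesions, q the share of biopsies from non-avid lesions, and rho the effect in non-avid lesions relative to avid ones. The expected mean change is

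D × [1 − q(1 − rho)].

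The documents give neither q nor rho. Assumed ranges are q = 1/6 to 3/6 (6 patients per schedule) and rho = 0 to 1.

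| Non-avid biopsies | rho = 0 | rho = 0.5 | rho = 1 |
|---|---|---|---|
| 1 of 6 | 83% of D | 92% | 100% |
| 2 of 6 | 67% | 83% | 100% |
| 3 of 6 | 50% | 75% | 100% |

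Example: 2 of 6 with rho = 0.5 gives 1 − (2/6)(0.5) = 0.83.

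**Step 3. Spurious gap between schedules.** With the same D in each schedule, the gap of Schedule 3 over Schedule 1 or 2 is

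D × (q12 − q3)(1 − rho).

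| q12 v q3 | rho = 0 | rho = 0.5 | rho = 1 |
|---|---|---|---|
| 1/6 v 0 | 0.17 D | 0.08 D | 0 |
| 2/6 v 0 | 0.33 D | 0.17 D | 0 |
| 3/6 v 0 | 0.50 D | 0.25 D | 0 |
| 2/6 v 1/6 | 0.17 D | 0.08 D | 0 |

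The gap vanishes if the shares are equal or the effects are equal. These formulas are for means; a median need not move by the same fraction.

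**Step 4. How easily a non-avid biopsy could arise.** If each biopsied lesion independently has probability p of being non-avid, the chance of at least one among 6 is 1 − (1 − p)^6: 27%, 47% and 74% for assumed p of 5%, 10% and 20%.

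**Step 5. Scale.** Six against six has 80% power (two-sided 0.05, normal approximation) only for a difference of about 1.6 SD. The schedule comparison is weak whichever lesions are sampled.

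**Step 6. What an edit can still reach.** Section 1.7.1 reports 14 Part A patients by June 1, 2020, and Section 3.2 fills the schedules in sequence, 6 at a time. Without replacements, 6 + 6 = 12 places in Schedules 1 and 2 were filled and 14 − 12 = 2 patients were on Schedule 3.

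**The case against.** The strongest reply has four parts.

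- **The difference is one of priority only.** Schedule 3 also permits a non-avid lesion, every patient has at least three avid lesions, and where only one lesion can be reached the rules give the same result. This stands. The rules diverge only when both kinds are accessible and the non-avid one is taken.
- **Zero effect in non-avid lesions is the worst case and runs against the trial's hypothesis.** Section 1.3 hopes for response to spread to PSMA-negative lesions, and Section 1.5 invokes the abscopal effect. This stands against any fixed magnitude. It does not count against recording avidity, because spread can be shown in the tissue data only if the biopsied lesion's avidity is known.
- **The consequence is limited.** The timing comparison is exploratory and non-randomised, has 6 patients per schedule and no planned test, and is already confounded by biopsy timing and pembrolizumab exposure. Circulating T cell measures do not depend on the lesion. All of this stands, but the immunologic data still inform the schedule choice.
- **The edit comes late, and the copied sentence is incomplete.** Schedules 1 and 2 of Part A were probably full, and the Schedule 3 sentence does not say whether an avid bone lesion outranks a non-avid soft-tissue one. Both points stand and shape the fix. If Schedule 1 or 2 is chosen, Part B would also follow a different lesion rule from the Part A patients on that schedule, which is a further reason to report by avidity.

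**Conclusion.** The inconsistency is certain: the avid-first instruction appears in one calendar of three, with no reason given for the difference. Its effect is possible but of unknown size. Dilution requires some non-avid biopsies and a smaller effect in them; a spurious difference between schedules also requires unequal non-avid shares. Over the assumed ranges the gap runs from zero to half of the avid-lesion change. The upper end needs 3 of 6 against 0 of 6 and no effect at all in non-avid lesions.

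A reader might infer that the Schedule 1 and 2 tissue results are in fact diluted, and biased against an all-avid Schedule 3 cohort. The documents do not support that. They give neither the shares nor the relative effect, and Schedule 3 allows non-avid lesions as a fallback. Nor would a common lesion rule make the schedules comparable, because the timing and pembrolizumab differences would remain. The point concerns biopsy measures only and does not touch the blood measures.

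**What to change.** 1. Use one lesion-selection rule in all three calendars and in Part B, by carrying the existing Schedule 3 sentence into footnote 7 of 5.2 and 5.3. State in all three how it ranks against the soft-tissue-before-bone preference. This mainly protects Part B.
2. For every biopsied lesion, at screening and at follow-up, record whether it was avid on the baseline PET (SUVmax against liver, as in inclusion 4). Do this retrospectively for Part A, where it is the only step that still helps patients already biopsied.
3. In Section 8.4.3, report tissue immune change for all biopsies and by lesion avidity, and show the avid share next to any comparison of schedules.

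The cost is one sentence in two footnotes, a line on precedence in all three, and one variable read from a scan that eligibility already requires. No extra procedure is needed. The drawback is small subgroups in the by-avidity summary, which should stay descriptive.
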